1. LIST OF ABBREVIATIONS

Abbreviation or Term	Definition/Explanation
ALT	alanine aminotransferase
AST	aspartate aminotransferase
AUC	area under the concentration-time curve
BSA	body surface area
BUN	blood urea nitrogen
CR	complete response
CT	computed tomography
CTCAE	Common Terminology Criteria for Adverse Events
DLT	dose limiting toxicity
DOR	duration of response
ECG	Electrocardiogram
ECOG	Eastern Cooperative Oncology Group
EOS	end of study
ESEC	Efficacy and Safety Evaluation Committee
HbA1c	hemoglobin A1c
LDH	lactate dehydrogenase
MedDRA	Medical Dictionary for Regulatory Activities
MRI	magnetic resonance imaging
ORR	objective response rate
PD	progressive disease
PK	pharmacokinetic
PR	partial response
PT	preferred term
QTc	corrected QT interval
QTcB	corrected QT interval by Bazetts formula
QTcF	corrected QT interval by Fridericias formula
RBC	red blood cell
Rd	lenalidomide and dexamethasone
sCR	stringent complete response
SD	stable disease
SOC	system organ class
TEAE	treatment-emergent adverse event
VGPR	very good partial response
WBC	white blood cell

3. INTRODUCTION

The purpose of this statistical analysis plan is to provide details of the statistical analyses that have been outlined within the protocol for MLN9708 study TB-MC010034. The scope of this plan includes the final analysis that is planned and will be performed by the Biostatistics department or designee.

4. STUDY OBJECTIVES

4.1 Primary Objective

To evaluate the tolerability, safety, and pharmacokinetics of MLN9708 alone or in combination with lenalidomide and dexamethasone (Rd) in patients with relapsed and/or refractory multiple myeloma.

4.2 Secondary Objective

To evaluate the antitumor activity of MLN9708 in patients with relapsed and/or refractory multiple myeloma.

5. STUDY OVERVIEW

5.1 Summary of Study Design

This is a phase 1, multicenter, single-arm, open-label, dose-escalation study to evaluate the tolerability, safety, and pharmacokinetics of MLN9708 administered alone or in combination with Rd in patients with relapsed and/or refractory multiple myeloma.

This study consists of the following 4 cohorts.

- Cohort 1: MLN9708 4.0 mg
- Cohort 2: MLN9708 4.0 mg + Rd
- Cohort 3: MLN9708 5.5 mg
- Cohort 4: MLN9708 5.5 mg + Rd

Three subjects will be enrolled sequentially from cohorts 1 (MLN9708 4.0 mg alone) to 4. If dose-limiting toxicity (DLT) occurs in 1 subject during DLT-assessment period, 3 additional subjects will be enrolled in the applicable cohort to evaluate the tolerability in a total of 6 subjects. If DLT occurs in 2 of the 3 subjects, the given dosage is considered intolerable. If DLT occurs in 2 of the 6 subjects, the sponsor will determine the tolerability to the given dosage after discussing with the Efficacy and Safety Evaluation Committee (ESEC).

[figure not shown]
The sponsor will evaluate the tolerability of MLN9708 on the basis of the safety data including DLT incidences during the DLT-assessment period. The sponsor will decide whether the next cohort will be studied and the dose of the next cohort in consultation with the ESEC, if necessary. If the current cohort is considered tolerable, the next cohort will be in the order of cohorts 2 (MLN9708 4.0 mg + Rd), 3 (MLN9708 5.5 mg alone), and 4 (MLN9708 5.5 mg + Rd). Even if a dosage is considered tolerable and transition to the next cohort is considered feasible, the next cohort may not be studied based on the results of the overseas clinical studies and the current study.

The additional written informed consent for extended treatment will be obtained before the first dose of MLN9708 in Cycle 2 from the subjects who meet the criteria for beginning the next cycle of treatment and have no safety concern. Subjects who do not give the consent will undergo end of study (EOS) visit on 29 days after the last dose of MLN9708 in Cycle 1. The subjects giving the consent can continue the study treatment up to 12 cycles unless they meet the criteria of subject removal including evidence of progressive disease (PD) and intolerable toxicity. Subjects may remain on treatment after the 12 cycles if the investigator considers it beneficial for the subjects.

All subjects should undergo EOS visit on 29 days after the last dose of MLN9708.

The overall study design is described in Table 5-1. "Study Design and Treatment Schema".

Table 5-1. Study Design and Treatment Schema

5.2 Sample Size Considerations

The planned number of subjects in this study is 3 to 6 for each cohort (12 to 24 in total).

The sample size was selected with reference to the preceding overseas clinical studies and the “Anti-Malignant Tumor Drug Clinical Assessment Guidelines” (PFSB/ELD Notification No. 1101001, dated November 1, 2005). The sample size was not selected based on a statistical rationale.

6. STUDY ENDPOINTS

6.1 Primary Endpoint

- DLTs, adverse events, body weight, vital signs, 12-lead electrocardiograms (ECGs), laboratory tests.
- MLN2238 plasma concentration.

6.2 Secondary Endpoints

- Number of subjects achieving CR, VGPR, and PR.

7. ANALYSIS SETS

7.1 Safety Analysis Set

The safety analysis set will consist of all subjects who received at least one dose of study treatment. Subjects will be analyzed according to the treatment received. Safety analysis set will be used for all safety analyses unless otherwise specified.

7.2 Dose Limiting Toxicity (DLT) Analysis Set

The DLT analysis set will consist of all subjects who experienced at least one DLT during DLT-assessment period (i.e., from the first dose to start of dose in cycle 2), or who received 3 planned doses of MLN9708 and completed the DLT-assessment period. DLT analysis set will be used for DLT analyses.

7.3 Response Evaluable Analysis Set

The response evaluable analysis set will consist of all subjects who received at least one dose of study treatment, have measurable disease at baseline, and at least one post-baseline tumor assessment. Response evaluable analysis set will be the primary analysis set for the analyses of response.

7.4 Pharmacokinetic (PK) Analysis Set

The PK analysis set will consist of all subjects who had at least one evaluable concentration data and received at least one dose of study treatment. Unless otherwise specified, the PK analysis set will be used for all PK analyses.

8. DATA HANDLING

8.1 Handling of Missing Data

Missing values by drop-out or error will be removed from analysis and not be imputed. However, estimation of pharmacokinetic parameters will be performed as much as possible, even if there are missing values. PK data below the lower limit of quantitation will be treated as “zero”.

8.2 Handling of Partial Date

For initial diagnosis or each last prior event (antineoplastic therapy, radiation therapy, bone marrow transplant or stem cell transplant, and any surgical procedures) with the dates that are partially missing, the following rules will be applied:

- If only month and year are provided, the 1st of the month will be used if the year and the month are the same as those for the first dose of study treatment. Otherwise, the 15th will be used.
- If only year is provided and it is the same as the year of the first dose of study treatment, the 1st of January will be used. Otherwise, the 1st of July will be used.

The listing will be prepared based on original date (e.g., 2007/01/UN / 2007/UN/UN).

8.3 Definition of Baseline Values

Unless otherwise specified, the baseline value is defined as the value collected at the time closest to, but prior to, the first dose of any study treatment.

8.4 Windowing of Visits

If some multiple values are observed in the same time window, the value on the closer day to the target date will be adopted. If the difference between the observed dates and the target date is same, later value is adopted for safety evaluation. However, the actual dates of these values should be used in the listings and individual plots.

9. STATISTICAL METHODS OF ANALYSIS

9.1 General Principles

- Tables will be tabulated by the following groups unless otherwise specified;
 - monotherapy treatment group
 - combination treatment group
 - total of all subjects
- Listings and figures are provided by treatment group unless otherwise specified.
- Continuous variables will be summarized descriptively using summary statistics (n, mean, standard deviation, median, max, and min).
- Categorical variables will be summarized using frequencies and percentages.
- The analyses will not be performed for N=1.
- The National Cancer Institute-Common Terminology Criteria for Adverse Events (CTCAE) Version 4.03 will be used for grading the adverse events and clinical laboratory abnormalities.
- International uniform response criteria for multiple myeloma (Durie et al, 2006) will be used for evaluating the tumor response.

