## **6.6 Cohort Transition and Early Stopping Guidelines**

### **6.6.1 Cohort Transition**

Three subjects will be initially enrolled into each dose level in order starting with cohort 1. The sponsor will evaluate the tolerability of MLN9708 dosage in each cohort on the basis of the DLT incidences in consultation with the ESEC, if necessary.

Even if a dosage is considered tolerable and transition to the next cohort is considered feasible, the next cohort may not be studied based on the results of the overseas clinical studies and the current study.

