- Subject incidence of treatment-related adverse events leading to permanent discontinuation of study treatment by preferred term in descending order of frequency (Safety analysis set)
- Subject incidence of dose limiting toxicities by preferred term in descending order of frequency by safety evaluation committee in cycle 1 (DLT analysis set)

A subject counts once for each SOC and PT for its worst grade.

All “by SOC and PT” and “by PT” tabulations are prepared by descending order of frequency for total of treatment groups and by alphabetical order.

Serious adverse event that occurred prior to first dose of MLN9708 will be presented in the listing.

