13. DOCUMENT HISTORY

Version	Date	Author	Remarks
1.0	11 April 2012	PPD	Original version
2.0	12 February 2014	PPD	
"BSA" and "EOS" have been added to the list in section 1.
 
Description of the study design has been corrected in section 5.1.
 
Some descriptions have been corrected in section 7, 8, and 9.
 
"8.2 Handling of Partial Date" has been added in section 8.
 
"total of monotherapy treatment groups" and "total of combination treatment groups" have been deleted in section 9.1.
 
To use "International uniform response criteria for multiple myeloma (Durie et al, 2006)" for evaluating the tumor response has been added in section 9.1.
 
"MLN9708 completion", "Lenalidomide completion", "Dexamethasone completion", and "Study completion" have been deleted from items for subject disposition in section 9.2.1.1.
 
"Study treatment completion" has been added to items for subject disposition in section 9.2.1.1.
 
"Study status" has been added to items for subject disposition in section 9.2.1.1.
 
Methods have been changed in section 9.2.1.2.
 
"BSA" and formula for calculating it have been added to items for demographic and baseline characteristics in section 9.3.1.1.
 
"Duration from last prior antineoplastic therapy to first dose", "Duration from last prior radiation therapy to first dose", "Duration from last prior bone marrow transplant or stem cell transplant to first dose", "Duration from last prior any surgical procedures to first dose", and formula for calculating them have been added to items for disease characteristics in section 9.3.1.1.
 
"Evidence of lytic bone disease" has been changed to "Evidence of lytic bone disease at initial diagnosis" in section 9.3.1.1.
 
"Evidence of extramedullary disease" has been changed to "Evidence of extramedullary disease at initial diagnosis" in section 9.3.1.1.
 
"Serum creatinine and by category" has been deleted

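### SAP 9.1 sets table columns by regimen with no dose and leaves treatment group undefined, so if a 5.5 mg cohort opens the summary tables may mix 4.0 mg and 5.5 mg subjects

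*SAP*

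**What the plan says.** SAP 9.1 gives the default layout: "Tables will be tabulated by the following groups unless otherwise specified". Three groups follow: a monotherapy group, a combination group (both singular, neither with a dose) and all subjects. Listings and figures are to be given by treatment group, and the SAP defines that term nowhere. SAP 9.4.2.2 relies on it again when it orders the adverse event tables "by descending order of frequency for total of treatment groups and by alphabetical order".

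SAP 5.1 says "This study consists of the following 4 cohorts": 4.0 mg, 4.0 mg + Rd, 5.5 mg and 5.5 mg + Rd. SAP 5.2 plans 3 to 6 subjects in each and 12 to 24 overall. SAP 5.1 also says that "the next cohort may not be studied based on the results of the overseas clinical studies and the current study".

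The protocol takes its decision at cohort level (6.6.1): "The sponsor will evaluate the tolerability of MLN9708 dosage in each cohort on the basis of the DLT incidences". DLTs and adverse events are primary endpoints in both documents. The SAP's DLT table is specified as "Subject incidence of dose limiting toxicities by preferred term in descending order of frequency", with no cohort or dose in its title.

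**The concern.** The unit of decision is the cohort, meaning a dose within a regimen. The unit of the default table, as 9.1 is worded, is the regimen. If a 5.5 mg cohort opens and the wording is followed literally, subjects on two doses share a column in the DLT, adverse event, laboratory, exposure and response tables. Anyone wanting the results of a pooled cohort would have to rebuild them from the SAP 10 listings. Protocol 1.7.4 gives a reason to expect the doses to differ. In the weekly monotherapy study, 2 of 6 subjects had Grade 3 events at the equivalent of 5.5 mg, and no Grade 3 or higher events were reported at the equivalent of 4.0 mg.

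**Working it through.** **1. The plan's own figure.** Four cohorts of 3 to 6 subjects give 4 × 3 = 12 and 4 × 6 = 24, which matches SAP 5.2. The stated size therefore assumes all four cohorts. A column holding both cohorts of one regimen would contain 2 × 3 = 6 to 2 × 6 = 12 subjects.

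**2. Does any table override the default?** Tabulations named in the SAP, leaving out line plots:

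- 9.2 and 9.3: enrollment and disposition 2, analysis sets 1, deviations 1, baseline 2. Total 6.
- 9.4 and 9.5: exposure 6, adverse events including DLTs 15, laboratory 10, ECG 4, vital signs and weight 2, ECOG 1, response 1. Total 39.

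None of the 6 + 39 = 45 names a cohort or a dose, so the exception allowed in 9.1 is never used to separate 4.0 mg from 5.5 mg.

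**3. Which columns mix doses, reading 9.1 as one column per regimen?**

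| Cohorts opened | Monotherapy column | Combination column | Total column |
|---|---|---|---|
| 1, 2 | 4.0 mg only | 4.0 mg + Rd only | one dose |
| 1, 2, 3 | 4.0 and 5.5 mg | 4.0 mg + Rd only | two doses |
| 1, 2, 3, 4 | 4.0 and 5.5 mg | 4.0 and 5.5 mg, each + Rd | two doses |

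**4. DLT illustrations (counts assumed).**

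- 0/3 at 4.0 mg and 2/3 at 5.5 mg pool to (0 + 2)/(3 + 3) = 2/6 = 33%, exact 95% interval 4% to 78%. Protocol 6.6.1 classes 2 of 3 as intolerable. At a single dose, 2 of 6 is instead the result on which the sponsor consults the ESEC. The pooled cell does not show which of these it is, although a reader who learned the cohort sizes elsewhere could work back in this smallest case.
- 2/9 = 22% (exact 95% interval 3% to 60%) is harder to unpick. It fits 0/3 at 4.0 mg with 2/6 at 5.5 mg. It also fits 2/6 at 4.0 mg, judged tolerable after consultation, with 0/3 at 5.5 mg.

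**5. Exposure illustration (assuming full dosing).** SAP 9.4.1.1 defines dose intensity as total dose divided by cycles treated. With three doses per cycle (protocol 6.3.1) it is 3 × 4.0 = 12.0 mg/cycle or 3 × 5.5 = 16.5 mg/cycle. For cohort sizes n1 (4.0 mg) and n2 (5.5 mg) from 3 to 6:

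- Pooled mean = (12.0·n1 + 16.5·n2)/(n1 + n2). This is 13.5 at (6, 3), 14.25 at equal sizes and 15.0 at (3, 6).
- Pooled SD = 4.5·√[n1·n2/((n1 + n2)(n1 + n2 − 1))]. This runs from 2.25 at (3, 6) or (6, 3) to 2.46 at (3, 3).

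The pooled mean is a level scheduled for nobody. Each cohort's own SD would be 0, but only because full dosing is assumed; the protocol allows reductions from Cycle 2. Relative dose intensity and dosing compliance are not distorted in this way, since both are 100% at full dosing. Nor are scheduled lenalidomide (25 × 21 = 525 mg/cycle) and dexamethasone (40 × 4 = 160 mg/cycle), which are the same in cohorts 2 and 4.

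**The case against.** The strongest reply is that the SAP never planned to pool. Its version log records that v2.0 deleted "total of monotherapy treatment groups" and the matching combination total from 9.1. It would be odd to remove regimen totals and mean the lines left behind to be regimen totals. Two explanations fit the deletion at least as well. The remaining lines may stand for the individual dose groups within each regimen. Or one group per regimen was expected, which made subtotals redundant. The timing suits the second: protocol version 3 of 4 December 2013 added that a next cohort may not be studied, and SAP v2.0 followed on 12 February 2014. Neither explanation pools doses. This stands as a limit on the point. A log of superseded text cannot define the current term, but it does prevent anyone from saying that pooling is the plan.

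It can also be said that much is protected. That is correct. Escalation is decided per cohort under protocol 6.6.1. SAP 10 plans subject listings, including DLTs by committee and by investigator. Line plots are by subject. Protocol 10.4.3 asks for PK summaries by dose. With 3 to 6 subjects per cohort, the listings can recover what a table does not show. The protocol's own safety section does not require tables by cohort.

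A reader might infer that once any 5.5 mg cohort opens, no dose can be seen on its own. The documents do not support that: with only cohort 3 added, the combination column still shows 4.0 mg + Rd alone.

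**Conclusion.** The point holds as a minor one. Treatment group is undefined, and the singular, dose-free wording of SAP 9.1, read alone, gives one column per regimen. On that reading the specified DLT, adverse event, laboratory, exposure and response tables would not separate the pooled cohorts.

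The effect rests on two conditions: a 5.5 mg cohort opens, and 9.1 is applied by regimen. If only cohorts 1 and 2 run, or if the columns are drawn per cohort, the effect is nil. The DLT figures above use assumed counts, and the exposure figures assume full dosing, so both only illustrate the mechanism.

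It would be tempting to conclude that the sponsor chose to pool doses, or that the tolerability decisions are compromised. The version log leaves the first open, and the per-cohort rules in protocol 6.6.1 rule out the second.

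**What to change.** In SAP 9.1, define treatment group as each cohort opened (MLN9708 starting dose within regimen). Use it as the table column alongside the overall total, and let the same definition govern listings and figures. Regimen subtotals are optional.

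Cost: one short edit, with no new data and no protocol change. Tables now have 3 columns. With all four cohorts open they would have 4 + 1 = 5, which is two more, or 4 + 2 + 1 = 7 with both regimen subtotals, which is four more. With only cohorts 1 and 2 open the count stays at 2 + 1 = 3. The columns would be sparse, at about 3 to 6 subjects, and the 9.1 rule against analyses at N=1 may blank a cell or a column, for example where few subjects are response-evaluable.

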9.2 Enrollment and Disposition of Subjects

9.2.1 Subject Disposition

9.2.1.1 Items

Items for subject enrollment

- Subjects screened
- Subjects enrolled

Items for subject disposition

- MLN9708 administration: [Received, Never received]
- Lenalidomide administration: [Received, Never received]
- Dexamethasone administration: [Received, Never received]
- Study treatment completion: [Ongoing, Discontinuation, #Reasons]
- Study status: [Ongoing, Completed Safety Follow-up, Discontinued Without Safety Follow-up]

9.2.1.2 Methods

The following tabulations will be prepared:

- Subject enrollment (Subjects screened)
- Subject disposition (Subjects enrolled)

9.2.2 Analysis Sets

9.2.2.1 Items

Every analysis set defined in Section 7 “ANALYSIS SETS”.

9.2.2.2 Methods

The number of subjects included in and excluded from each analysis set will be tabulated for all subjects enrolled.

9.2.3 Protocol Deviations and Treatment Compliance

9.2.3.1 Items

The following categories of important protocol deviations:

- EN : Entered study even though entry criteria was not satisfied
- XM : Received an excluded concomitant treatment
- NW : Developed withdrawal criteria but was not withdrawn
- TA : Received the wrong treatment or incorrect dose
- TC : Other Treatment Compliance

- OS : Off-schedule procedures (other than TA or TC)
- MD : Missing data (other than TA or TC)
- OT : Other Deviations

9.2.3.2 Methods

The number of subjects with any important protocol deviations and each important protocol deviation will be tabulated for all subjects enrolled.

9.3 Demographic and Other Baseline Characteristics

9.3.1.1 Items

Items for demographic and baseline characteristics

- Sex
- Age
- Age group: [< 65 , ≥ 65 years]
- Height
- Weight
- Body Surface Area (BSA)
BSA will be calculated using the following formula:
 - $BSA (m^2) = Height (cm)^{0.5} * Weight (kg)^{0.5} / 60$
- Eastern Cooperative Oncology Group (ECOG) performance status: [0, 1, 2]
- Medical and surgical history: [Yes, No]

Items for disease characteristics

- Disease type: [IgG (Kappa, Lambda), IgA (Kappa, Lambda), IgD (Kappa, Lambda), IgE (Kappa, Lambda), IgM (Kappa, Lambda), Other]
- Stage at initial diagnosis (Durie-Salmon Stage): [IA, IB, IIA, IIB, IIIA, IIIB, Unknown]
- Stage at initial diagnosis (International Staging System Stage): [I, II, III, Unknown]
- Duration from initial diagnosis to first dose
- Duration from last prior antineoplastic therapy to first dose
- Duration from last prior radiation therapy to first dose
- Duration from last prior bone marrow transplant or stem cell transplant to first dose
- Duration from last prior surgical procedures to first dose
Duration will be calculated using the following formula:
 - $Duration (months) = (Date of first dose - Date of initial diagnosis or each last prior event) * 12 / 365.25$
- Evidence of lytic bone disease at initial diagnosis: [Yes, No, Unknown]
- Evidence of extramedullary disease at initial diagnosis: [Yes, No, Unknown]
- Stage at study entry (Durie-Salmon Stage): [IA, IB, IIA, IIB, IIIA, IIIB, Unknown]

- Stage at study entry (International Staging System Stage): [I, II, III, Unknown]
- Serum creatinine (in summary statistics)
- Serum creatinine by category: [≤ 2 , > 2 mg/dL]
- Creatinine clearance by category: [< 30 ; $30 \leq$, < 60 ; ≥ 60 mL/min]
Creatinine clearance will be calculated using the Cockcroft-Gault formulas as follows:
 - For male subjects:
Creatinine clearance (mL/min) = $(140 - \text{Age [years]}) * \text{Weight (kg)} / (72 * \text{Serum creatinine [mg/dL]})$
 - For female subjects:
Creatinine clearance (mL/min) = $0.85 * (140 - \text{Age [years]}) * \text{Weight (kg)} / (72 * \text{Serum creatinine [mg/dL]})$
- Kappa/Lambda ratio by category: [< 1 , ≥ 1]
- Serum M-protein (total M-protein)
- 24 hour urine M-protein (urine total M-protein)
- Beta-2-microglobulin by category: [< 2.5 ; $2.5 \leq$, ≤ 5.5 ; > 5.5 mg/L]
- Albumin by category: [< 3.5 , ≥ 3.5 g/dL]
- Corrected calcium
Corrected calcium will be calculated using the following formulas:
 - Corrected calcium (mmol/L) = $0.25 * (\text{Serum calcium [mg/dL]} - 0.8 * (\text{Albumin [g/dL]} - 4))$, when Albumin (g/dL) is ≤ 4 .
 - Corrected calcium (mmol/L) = $0.25 * \text{Serum calcium (mg/dL)}$, when Albumin (g/dL) is > 4 .
- Subjects with bone marrow aspirate: [Available, Unable to detect, Not available]
- Bone marrow aspirate results (% Plasma cells)
- Skeletal survey results at screening: [Within Normal Limits, Abnormal not clinically significant, Abnormal clinically significant]
- Lytic bone lesions at screening: [Yes, No, Indeterminate]
- Chest X-Ray results at screening: [Not done, Done (Within Normal Limits, Abnormal not clinically significant, Abnormal clinically significant, Not evaluated/Inevaluable)]
- CT/MRI results at screening: [Within Normal Limits, Abnormal not clinically significant, Abnormal clinically significant]
- Plasmacytomas at screening: [Yes, No, Indeterminate]
- Prior antineoplastic therapy: [Yes, No]
- Prior radiation therapy: [Yes, No]
- Prior bone marrow transplant or stem cell transplant: [Yes, No]
- Prior surgical procedures: [Yes, No]

